9.4.4 Vital Signs, Physical Examinations and other Assessments

At Screening and prior to each dosing, blood pressure, pulse, respiratory rate and temperature (subjects should be in rest and in supine position at least 10 minutes before vital signs measurement; and they should be in rest and in supine position during the vital signs measurements) will be measured.

In case it is necessary to be measured vital signs for some adverse event and coincide with the scheduled signs, the vital signs will be measured according to the current subject's condition until they are resolved, then the scheduled vital signs will be measured.

These values should be within the normal range (SBP between 80 and 129 mmHg and DBP between 50 and 89 mmHg, heart rate between 50 and 100 beats per minute) in order the subject is allowed to keep on participating in the study. Same measurements will be made during all shifts following dosing at each one of the visits. Vital signs will be measured as shown in the following:

Record of Vital Signs

First Visit	Second Visit	Third Visit	Fourth Visit
Admission	Admission	Admission	Admission
Pre-dose	Pre-dose	Pre-dose	Pre-dose
Morning shift (approximately 4 h post-dose)			
Evening shift (approximately 8 h post-dose)			
Night shift (approximately 12 h post-dose)			
24 and 32 h post-dose			
Discharge (48 h post-dose)			
Ambulatory samples (72, 96, 120, 144 and 168 h post-dose)	Ambulatory samples (72, 96, 120, 144 and 168 h post-dose)	Ambulatory samples (72, 96, 120, 144 and 168 h post-dose)	Ambulatory samples (72, 96, 120, 144 and 168 h post-dose)

In the event any subject has clinically significant changes out of normal ranges for blood pressure and pulse during confinement post-dose, he/she will be observed by the medical staff. Supportive measures, as appropriate, will be taken according to the current subject's condition until they are resolved. If change persists, continuation in the study will be considered by the Principal Investigator.

9.5 Pharmacokinetics

Twenty two (22) 10-mL samples of venous blood will be taken per period with catheter or venipuncture for the measurement of drug's plasma concentration: 0.00 (Pre-dose, control), 0.5, 1.0, 2.0, 3.0, 4.0, 5.0, 6.0, 7.0, 8.0, 10.0, 12.0, 16.0, 24.0, 28.0, 32.0, 48.0, 72.0, 96.0, 120.0, 144.0 and 168.0 h following administration.

9.5.1 Body Fluids

Pharmacokinetics Blood Samples

- ✦ One blood sample will be collected per period at times established in the schedule. Test tubes with sodium heparin, specifically designed for venipuncture, will be used.
- ✦ Each sample will be 10 mL. Blood withdrawn to clean catheter should be disposed prior to the blood sample collection (purge). Blood volume to be withdrawn by visit will be of 220 mL approximately (440 mL a month), 880 mL of blood in total at the end of the study.
- ✦ A \pm 1 minute window is allowed for sampling during absorption and distribution phase, and up to \pm 3 minutes during the excretion phase.
- ✦ Each sample will be centrifuged at 2450 x g for 5 minutes at 4 °C [39.2 °F] (\pm 2 °C [35.6 °F]).
- ✦ Resulting plasma volume will be transferred into 1.5 or 2 mL cryotubes each.
- ✦ Plasma tubes will be perfectly identified with Study No. (##), Case No. (C##), Sample No. (S##) and Visit No. (V#). They will be kept deep frozen at a temperature lower than or equal to - 40 °C or lower, according to the standard operating procedures, code: PPD [REDACTED] Early organization for the conduct of an interchangeability and biocomparability study; and PPD [REDACTED] Processing and shipment of biological samples for interchangeability and biocomparability studies, PPD [REDACTED] Samples transportation from the clinical unit to the analytical unit; until their delivery at the analytical unit.

Samples Shipment

To ensure transportation conditions of biological samples from the laboratory, where they were processed for freezing and storage, to the analytical unit do not affect samples' stability, it is essential to comply with the following guidelines:

- ✦ The Study Principal Investigator or the Sub-Investigator will define shipment's date and time in accordance with the analytical unit, as well as the transportation to be used and approximate time for itinerary.
- ✦ Mechanism of control and security for samples shipment will be defined by the person in charge of transportation in agreement with the Principal Investigator or Sub-Investigator.
- ✦ Samples Processing Responsible or designated person will sign a list of material to be shipped, with a detailed description by subject for tubes quantity and codes.
- ✦ An internal temperature reading system will be available in the fridge. A reading will be made at least every 30 minutes with its appropriate record.

- ✦ In addition, reading at the moment of departure of the material from the samples processing area, as well as a reading at the reception at the analytical unit will be made.
- ✦ Samples transportation is the responsibility of the clinical unit where samples collection and processing took place.
- ✦ Delivery will be made personally, by a member of the Clinical Unit.
- ✦ Samples should arrive deep frozen (- 20 °C [- 4.0 °F] as maximum) at the moment of the container bags check.
- ✦ A temperature log will be included in the trial master file.

Samples Receipt, Check and Storage by the Analytical Unit

- ✦ Person responsible for the study or designated person from the analytical area will receive samples (along with documentation) and check 100 % with the assistance from analysts and Quality Assurance. They will record any remarks on the appropriate form. Once review is finished the person responsible for the study or designated person will store samples in the ultra-freezer documenting it on the equipment's notebook.
- ✦ Quality Assurance will confirm accuracy and reliability of operations.

Samples which do not meet acceptance criteria will be rejected. In addition to those which don't have documentation along with them. In such instances, the clinical unit should be informed about the reason why samples were rejected. Rejected biological specimens will be kept at the analytical unit meanwhile the analytical unit and the clinical unit make an agreement about their disposition.

Handling of Biological Specimens by the Analytical Unit

Biological specimens will be handled and processed as described in the appropriate analytical technique.

Biological Specimens Disposition

As agreed with the Sponsor or 30 calendar days following the final report, samples will be removed from the ultra-freezer and will be stored in a transient warehouse for infectious biological hazard residues until they are collected for their final disposition by an authorized designated company.

Ultra-frozen Samples Labelling

Cryotubes will be identified with labels according to the standard operating procedure, code: **PP** , Early organization for the conduct of an interchangeability and biocomparability study. Each cryotube will state the study number, subject's number, period and number of samples specified in the protocol. Labels will be digitally designed and printed using thermal printer.

Label and printing type will ensure that that printing and adhesion resist several freezing and thaw cycles.

9.5.2 Pharmacokinetic calculations

Bioanalysis will be performed by analytical unit from the PPD [REDACTED].

PK parameters of Metformin and Gliclazide's plasma concentrations will be calculated and evaluated by the analytical unit from the PPD [REDACTED], according to their standard operating procedures and in accordance with the NOM-177-SSA1-2013.

Non-compartmental computation of PK parameters as well as descriptive statistical analysis for PK primary and secondary endpoints will be performed using Phoenix WinNonlin 6.3 software.

The primary PK variables will be calculated and listed for all subjects who provided sufficient concentration-time data.

9.6 Statistics

9.7 Sample Size

The sample size estimation is based on the CV intrasubject variability of both drugs. Because the pharmacokinetic and drug-drug interaction, evaluates changes in the bioavailability, the propose is the use the same determination for both aims.

The sample size is determined by the primary endpoint with the greatest variability under fasting conditions, AUC_{0-t} of Metformin (CV=23%). Assuming a mean treatment ratio of 0.95, and aiming at a power of 90% for the individual test, alpha=0.05 one-sided, 32 evaluable subjects are sufficient to demonstrate bioequivalence in the first step. The same arguments can be applied to the second step: Test absence of an effect of Gliclazide on the PK of Metformin, whereas the power for the third test is close to 100% with 32 subjects, due to the low variability of Gliclazide PK. Therefore, the overall power is still greater than 80% with 32 evaluable subjects. Considering a drop-out rate of approximately 20%, 40 subjects should be randomized.

According to NOM-177-SSA1-2013, this sample determination was realized with Chow & Wang (2001) equation

$$n \geq [t_{(\alpha, 2n-2)} + t_{(\beta, 2n-2)}]^2 \cdot \left(\frac{CV_{intra}}{\ln 0.8 - \ln \theta} \right)^2$$

Where:

$t(\alpha, 2n-2)$ and $t(\beta, 2n-2)$ considered the error α and β respectively

CV_{intra}: intra subject variability for crossover (or replicate crossover) study.

T_{theta}: 0.95: the target ratio in average BA between the two formulations expressed in percentage of the average reference

0.8: the least statistical power to detect (1-Power) differences between the Test and the Reference formulation (in this case the power expected is 90%)

9.8 Randomization

Forty male and female subjects will be included in this trial. Both sexes will be included with a minimum proportion of 30% for each sex at least 12 females and at least 12 males. Subjects will be randomly assigned to one of the 4 treatment sequences. Randomization of each subject to a treatment sequence will occur immediately before dosing on Day 1 of the first treatment period. The randomization list will be generated by the CRO based on the PPD [REDACTED] internal procedures and in compliance with the Mexican Official Standard NOM-177-SSA1-2013 using software in website www.randomization.com, in agreement with the sponsorures and in compliance with the Mexican Off drop-out before any drug administration, the new subject will be allocated the same randomization number. Subjects leaving the trial after they have received any of the drugs at least once might be replaced if the drop-out rate is higher than expected after discussion with the sponsor.

9.9 Outcome variables

9.9.1 Main outcome variable

To demonstrate Metformin/Gliclazide combination's bioequivalence at fixed dose as tablets (1.000 mg / 30 mg MR) compared to the concomitant administration of individual products (Metformin's tablet 1000 mg XR and Gliclazide tablets 30 mg MR), given as single dose to healthy volunteers in fasting state. The primary endpoints are AUC_{0-t} , $AUC_{0-\infty}$ and C_{max} for Metformin and Gliclazide.

9.9.2 Secondary outcome variables

The secondary outcome variable are volume of distribution K_e , half-life elimination, clearance, and median residence time all these parameters will be presented only for informative reasons for both medications.

9.9.3 PK Analysis Set

The PK Analysis Set will include all subjects who have completed the trial with adequate trial medication compliance, without any relevant protocol violations with respect to factors likely to affect the comparability of PK results, and with sufficient evaluable data to determine primary endpoints (AUC_{0-t}, AUC_{0-∞} and C_{max}) for both analytes. If subjects received concomitant medication for the treatment of an AE, their inclusion in the PK population needs to be discussed on a case-by-case basis.

All PK analyses will be based on this Analysis Set.

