7.3.3 Criteria for Randomization

Eligible subjects will be rechecked at the time of admission to the study center (Day -1).

Results of the procedures performed on Day -1 as detailed Section 9.1.1, must be available prior to randomization. All inclusion and exclusion criteria will undergo a final verification before randomization.

7.3.4 Criteria for Subject Withdrawal from trial:

Subjects can be withdrawn from the study, as per the Principal Investigator's judgment, for the following reasons:

In case continuous participation in the trial is detrimental for subject's health, as per Investigator's judgment.

1. Hypertension signs and symptoms which require pharmacological treatment.
2. Syncope or shock.
3. Severe adverse reaction.
4. Serious Adverse Event.
5. Concurrent diseases or concomitant treatments not allowed by the protocol.
6. Lack of discipline.
7. Lack of compliance with the diet.
8. Lost of two samples within absorption period or near to the C_{max} .
9. If vomit occurs within therapeutic dosing interval, research subject should be withdrawn from the study and removed from the statistical analysis.

10. If any of the participant subject, during wash-out period, takes alcoholic beverages, smokes tobacco, has xanthenes containing beverages or food (coffee, tea, cacao, chocolate, mate, coke drinks, etc.) grapefruit, grapes or citrus, or grilled food (charcoal) within 24 h prior to the recruitment in the admission phase, or using any drug known by affecting the study.
11. Subjects with positive results to the drugs screening such as: amphetamines, benzodiazepines, cocaine, metamphetamines, morphine and tetrahydrocannabinoids.
12. Positive pregnancy test (qualitative or quantitative) following the study drug dosing.
13. All cases where the Principal Investigator judges as lack of compliance to the protocol or which may risk final results.

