8.9 Assessment of Study Drug Compliance

Throughout dosing period, dose, full intake and time will be checked and recorded in the appropriate forms, according to the standard operating procedure, code: PPD [REDACTED]. Preparation and administration of drugs in clinical trials of interchangeability and biocomparability; PPD [REDACTED]. Randomization in an interchangeability and biocomparability clinical study

A subject is compliant with the treatment only if he/she completes all study periods.

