9.9.4 Safety Analysis Set

All the deviations must be justified with statistical or scientific evidence and any change to the original statistical plan must be reported, in the master file of the study and in the statistical pharmacokinetic report and final report of the study

Subject data will not be replaced, any data missing will be considered as a non-existing data and likewise data cannot be eliminated from the statistical analysis, except in the following cases:

Research subjects with pre-dose plasma concentrations in the biological matrix.

If the pre-dose concentration is lower than 5% of the C_{max} value in a subject, the subject's data can be included without adjustment in all measurements and pharmacokinetic calculations. In the cases where the pre-dose value is greater than 5% of C_{max}, the research subject must be eliminated from all study evaluations.

Data elimination due to vomiting or diarrhea

Data from research subjects who experimented vomiting or diarrhea during the course of a clinical study for immediate release products can be eliminated from the statistical analysis if the vomiting or diarrhea occurred before 2 times the median of T_{max} or 2 times the value of T_{max} obtained in the research subject during a given period.

A research subject with very low plasma concentrations for study drugs

As established by the Mexican Official STANDARD NOM-177-SSA1-2013, also research subjects that in a crossover design do not provide assessable data, both from test drug and reference drug, should not be included in the statistical analysis.

A research subject is considered to have very low concentrations if the AUC is lower than 5% of the geometrical mean of the reference medication AUC (must be calculated without inclusion of data of the research subject with atypical values).

Data exclusion due to this reason will only be accepted under scientific justification and previous review of the case by the Federal Commission for the Protection against Sanitary Risks (Comisión Federal para la Protección contra Riesgos Sanitarios, COFEPRIS).

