10.1 Definition of Protocol Deviations and Analysis Sets

All deviations should be justified with statistical or scientific data and any change to the original statistical plan should be documented, in the study master file and in the pharmacokinetics statistical report as well as in the final study report. Subjects' data will not be replaced. Any missing

data will be considered as non-existent data. Likewise, data cannot be removed from the statistical analysis, except in the following events.

▪ **Research Subjects with Pre-dose Concentrations in the Biological Matrix**

In the event pre-dose concentration is < 5 % of the C_{max} value for a research subject, subject's data can be included without any adjustment to measurement and pharmacokinetic calculations. When pre-dose value is > 5 % of the C_{max} , research subject should be removed from all study bioequivalence assessments.

▪ **Exclusion of data due to vomit or diarrhea.**

Data from research subjects who experience vomiting and diarrhea throughout the bioequivalence study for immediate release products can be removed from the statistical analysis if vomiting and diarrhea occur before 2 fold the median for t_{max} or 2 fold t_{max} value obtained from the research subject in a given period.

▪ **Research subject with very low plasma concentrations for study drugs.**

As established by NOM-177-SSA1-2013, research subjects in a cross designed who provide evaluable data for test drug and reference drug, or who do not have evaluable data in the single period of a parallel design, should not be either included in the statistical analysis.

It is considered that a research subject has very low concentrations, if the AUC is lower than 5 % of the geometric means for the reference drug's AUC (it should be calculated without including outliers). Exclusion of data due to this reason will only be accepted prior scientific rationale and review of the case by the COFEPRIS.

11 General Specifications for Statistical Analyses

Pharmacokinetic parameters (non-compartmental analysis) and statistical analysis for determining bioequivalence will be calculated using Phoenix WinNonlin 8.0 software.

The results of this trial will be reported using summary tables, figures, and data listings, as appropriate. All data will be summarized by treatment and/or scheduled time point, as appropriate.

12 Protocol Deviations

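### The PK Analysis Set admits only four-period completers with both analytes, although each confirmatory test contrasts two treatments, so usable test/reference pairs can be dropped for a missed period outside the contrast

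*Protocol*

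**What the plan says.** Protocol 9.9.3 defines one set for everything: "The PK Analysis Set will include all subjects who have completed the trial with adequate trial medication compliance". The subject must also have no relevant protocol violation and enough data to determine AUC0-t, AUC0-∞ and Cmax for both analytes. It then adds: "All PK analyses will be based on this Analysis Set".

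Protocol 8.9 gives the meaning of compliance: "A subject is compliant with the treatment only if he/she completes all study periods". Together, these make the PK set the four-period completers.

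Protocol sections 6 and 9.10.2 set three ordered tests, each contrasting the fixed tablet with one reference:

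- Step 1: co-administration, both analytes.
- Step 2: metformin alone, metformin only.
- Step 3: gliclazide alone, gliclazide only.

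Protocol 9.9.4 carries a safety-set heading but contains rules for the statistical analysis: "likewise data cannot be eliminated from the statistical analysis, except in the following cases". The cases listed are pre-dose concentration above 5% of Cmax, vomiting or diarrhea, and very low concentrations. Under the last it adds that subjects who "do not provide assessable data, both from test drug and reference drug, should not be included in the statistical analysis". SAP 10.1 has the same kind of closed list: "data cannot be removed from the statistical analysis, except in the following events". Neither list names failure to complete all periods. The SAP does not restate the completer set, and its section 9 declares no change to the planned analyses.

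**The concern.** The inclusion rule asks for more than any single test needs. A sequence 1 subject receives the fixed tablet in period 1 and co-administration in period 2. If that subject leaves before period 3, the step 1 pair is complete for both analytes, yet 9.9.3 excludes it. A sequence 3 subject who leaves after period 2 already has metformin alone and the fixed tablet, which is the step 2 pair, and is also excluded. The both-analyte condition works the same way: an unevaluable gliclazide endpoint removes a subject from the metformin-only step 2.

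Three things are at stake:

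- **Precision.** Valid within-subject pairs are not used.
- **Selection.** An adverse event or withdrawal during metformin alone can decide whether a subject counts in fixed tablet versus co-administration.
- **Pre-specification.** 9.9.3 and the removal rules in 9.9.4 and SAP 10.1 can yield different confirmatory populations, and the trial is open-label.

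**Working it through.** **Inputs.** Protocol 9.7 and SAP section 7: within-subject CV 23% (metformin AUC0-t), true ratio 0.95, one-sided alpha 0.05, power 90%, 32 evaluable, about 20% drop-out, 40 randomized. Limits 0.80 to 1.25 come from 9.10.2 and the sequences from 7.1.

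**1. Reproduce the plan's figure.** σw = √ln(1 + 0.23²) = 0.227 and ln 0.8 − ln 0.95 = −0.172. The printed formula has 2n − 2 degrees of freedom, so n is read as per sequence of a two-sequence design. At n = 16 the t quantiles on 30 df are 1.697 and 1.310:

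n ≥ (1.697 + 1.310)² × (0.227/0.172)² ≈ 15.8, so 16 per sequence, 32 in total.

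Using the raw CV instead of σw gives 17 per sequence, 34 in total. Exact power of the two one-sided tests (standard error σw√(2/n), n − 2 df, integrated over the variance estimate) is 90.4% at n = 32, the smallest n reaching 90%. Drop-out: 32/0.80 = 40. Overall power, taking the two metformin tests as independent and the third near 100%, is 0.904² ≈ 81.8%, in line with the stated value above 80%.

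**2. Which drop-outs hold a complete pair?** From the sequence table:

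| Last period completed | Step 1 | Step 2 | Step 3 |
|---|---|---|---|
| 1 | none | none | none |
| 2 | sequence 1 (1/4) | sequence 3 (1/4) | none |
| 3 | sequences 1, 2 (1/2) | sequences 1, 3 (1/2) | sequences 2, 3 (1/2) |

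**3. Apply this to 8 drop-outs.** The documents give only the overall rate; timing and spread are assumed. With two drop-outs per sequence, the completer rule keeps 32 in every row. Pairwise inclusion would keep:

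| All leave after period | Step 1 | Step 2 | Step 3 |
|---|---|---|---|
| 1 | 32 | 32 | 32 |
| 2 | 34 | 34 | 32 |
| 3 | 36 | 36 | 36 |

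If departures are spread evenly over the three times, the expected gain is (8/3) × (0 + 1/4 + 1/2) = 2 subjects for steps 1 and 2, and (8/3) × 1/2 ≈ 1.3 for step 3.

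**4. Convert to precision and power.** CI width scales with 1/√n, ignoring the small change in the t quantile. √(34/32) = 1.03 and √(36/32) = 1.06, so the completer CI is about 3% or 6% wider. Pairwise power at CV 23% and ratio 0.95:

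| n | Power |
|---|---|
| 32 | 90.4% |
| 34 | 92.0% |
| 36 | 93.3% |

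The largest gain is 93.3 − 90.4 = 2.9 points. If the residual is pooled over the three treatments carrying the analyte (2n − 4 df), the approximate figures are 91.0% at 32 and 93.7% at 36, a gain of 2.7 points. If all drop-outs happened to fall in the sequences that hold a pair, one step could in theory keep all 40 (95.3%); two per sequence is the more neutral assumption.

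**The case against.** The best defence is that the plan was sized for this rule. It needs 32 evaluable subjects and randomizes 40 so that 32 remain. A reader might infer that the rule leaves the trial underpowered. It does not: at 32 completers the single-test target is met, and the figures above are gains beyond it.

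A reader might also infer that 9.9.4 requires inclusion of anyone with test and reference data. Its sentence only says that subjects lacking such data are left out. That is a necessary condition, not a sufficient one, and it does not say which of the three references is meant. Taken literally, the closed list would also clash with the protocol-violation criterion in 9.9.3, so it does not single out non-completion. What stands is that the sections do not fit together. The SAP does not settle it, because its version of the test/reference sentence (10.1 and 12.2) has lost the negation for crossover designs.

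Nor do the documents support saying that lost pairs cannot be made good. Section 7.5 rules out replacing dosed subjects, but 9.8 allows it if drop-out is higher than expected, and 8.3 supplies replacement kits by sequence.

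Two further limits stand. The counts are upper bounds, since subjects excluded for vomiting, pre-dose concentration or a relevant violation stay out under any definition. And 9.10.2 does not say whether step 1 uses two treatments or pools a third into the residual. If pooled, that period informs the variance, although a mixed model can still include subjects with incomplete data.

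Finally, the withdrawal reasons in 7.3.4, including lost samples, are at the investigator's judgment. The point does not depend on changing them.

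**Conclusion.** The point holds as a modest improvement in efficiency and clarity. Sections 9.9.3 and 8.9 restrict every PK analysis to four-period completers with both analytes, which no single step requires. The rule is also hard to reconcile with the removal lists in 9.9.4 and SAP 10.1.

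With 8 drop-outs spread two per sequence, the cost is 0 to 4 otherwise evaluable subjects per step, a CI up to about 6% wider, and up to 2.9 points of power in a pairwise analysis. Planned power is not breached. Dependence of the loss on events outside the contrast is a plausible route to selection, but the documents give no basis for sizing a bias, and none is claimed. The firmer reason to act is that the confirmatory population should follow from one rule.

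**What to change.** In protocol 9.9.3 and in the SAP, define the PK set per comparison and analyte. A subject enters a step if the primary endpoints for that step's analyte or analytes are evaluable under both treatments compared and no other stated exclusion applies. In detail:

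- Remove the trial-completion condition from 9.9.3, and do not use the 8.9 compliance definition for this set.
- Make 9.9.3, 9.9.4 and SAP 10.1 agree, put the PK exclusion rules under a PK heading, and restore the missing negation in SAP 10.1 and 12.2.
- Keep four-period completers as a sensitivity analysis.
- Reconcile 7.5, 8.3 and 9.8 on replacement of dosed subjects.

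No change to the withdrawal criteria in 7.3.4 is proposed. The cost is wording only, with no extra subjects or procedures. The one drawback is that the number of subjects may differ between steps and must be reported for each.
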